Multiple strategies will be employed to recruit approximately 1200 lesbian, bisexual, and queer identified women residing in the United States to take part in the online LezParlay competition. Topics in the game will change from month to month and will feature stigma-coping behaviors and alcohol use, among other topics related to familiar lesbian and queer stereotypes (e.g., relationships, sex, identity, money, stress, and future plans). Over 8 monthly rounds of play, players will receive PNF on different topics and compete for cash prizes as they test the accuracy of their peer perceptions and discover how their own attitudes and behaviors compare to actual group norms. Importantly, in Round 3, when alcohol use is first assessed as a topic, a sub-sample of 500 players who report moderate drinking will be invited to participate in a LezParlay evaluation study. Participants who elect to take part in the study will be randomized to receive either PNF on alcohol use + coping behaviors, PNF on alcohol use + control topics, or PNF on control topics in subsequent rounds of the game. These study participants will be incentivized for playing remaining rounds and completing a follow-up survey about their experiences. Analysis of LezParlay efficacy will focus on longitudinal changes in alcohol use and coping behaviors associated with condition assignment and subsequent receipt of PNF among study participants. Analysis of feasibility associated with the gamified LezParlay format will focus on acceptability ratings and other feedback gathered from trial participants as well as basic application usage among the pool of players who elect to take part in the competition but do not participate in the study, and thus, are not incentivized for their completion of rounds.

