Qualtrics Research Suite's automated randomizer will be used to randomize evaluation study participants to a PNF condition at the point of study enrollment in round 3. Randomization will determine the sequence of topics on which participants will receive detailed results across intervention rounds 3 and 4: alcohol+coping, alcohol+control, or control only. Members of the research team will be blinded to participant condition assignment, and the study participants will not be aware that any sort of randomization was taking place. Rather, like in other rounds, when detailed results are sent players will be prompted to choose among 3 animated, graphical doors to determine the topics on which they will view detailed results. Although the results topics will be truly determined via chance in most rounds of the competition, the doors of evaluation study participants will be fixed to open to their randomly assigned feedback topics regardless of the door they selected in rounds 3 and 4. Upon completing the feedback survey at the end of the competition, participants will be debriefed regarding the study's research questions and the fixed sequences of health or control feedback they were randomized to receive in rounds 3 and 4. See Appendix D for the Debriefing Statement.

Replay Bonus Rounds 7 and 8.

The last 2 rounds of the competition, 7 & 8, will feature new question topics as well as previously assessed REPLAY BONUS topics which will allow all players to boost their scores by placing very large bets on a topic they already received feedback on and very small bets for topic on which feedback has not yet been delivered. PNF will be delivered for the new topics assessed in each round but will not be repeated for REPLAY BONUS topics. Instead a single screen will reveal the points earned from REPLAY BONUSES. Importantly, answers to REPLAY BONUS questions in Round 7 among intervention study participants' will act as the 2 month post-intervention follow-up for the purpose of the evaluation study RCT.

Competition Conclusion

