APPENDIX C

Norm questions to be featured in intervention rounds or potentially featured as control/filler questions in LezParlay Rounds

- Parallel Questions will also ask participants to report their own corresponding behavior/attitude/experience
- All questions will pipe the sexual identity (lesbian, bisexual, queer) and age-group (20s, 30s, 40s, 50s) of the user
- Some question topics and questions to appear in rounds will be voted on by players.
- Players can also submit their own questions to be voted on and potentially featured in some rounds.
- If any top voted user-submitted materially differ from those submitted in this exhaustive potential question list, we will submit an addendum to the IRB and get approval before any are featured in a round.

Alcohol Use Questions (Round 3 & Replay Bonus in Round 7)

During the past 2 months, on average, how many days per week did the Typical Lesbian drink alcohol?

- 0
- 1
- 2
- 3
- 4
- 5
- 6
- 7

During the past 2 months, on average, how many drinks did the Typical Lesbian have each time she drank?

- 0
- 1
- 2
- 3
- 4
- 5
- 6
- 7
- 8
- 9

10 or more

On the day she drank the MOST during the past 2 months, how many drinks did the Typical Lesbian have?

0

1

2

3

4

5

6

7

8

9

10

11

12 or more

HAD A HANGOVER OR ILLNESS

HAD PROBLEMS WITH FRIENDS OR FAMILY

GOT IN A PHYSICAL OR VERBAL FIGHT

PERFORMED POORLY AT WORK/SCHOOL

HAD PROBLEMS WITH GF/PARTNER

HAD PROBLEMS WITH MONEY

MISSED A SOCIAL ENGAGEMENT OR
EVENT

HAD AN UNWANTED OR REGRETTABLE
SEXUAL EXPERIENCE

During the past 2 months, how many of the 8 things above has the typical lesbian experienced due to drinking/partying?

0

1

2

3

4

5

6

7

Stigma Questions (Round 3 & Replay Bonus in Round 7)

During the past 2 months, what % of lesbians have been physically assaulted due to their sexual identity?
0% ----- 100%

During the past 2 months, what % of lesbians have been verbally harassed or threatened online or in person due to their sexual identity?
0% ----- 100%

During the past 2 months, what % of lesbians have overheard negative LGBTQ-related comments, jokes, or slurs?
0% ----- 100%

During the past 2 months, what % of lesbians have felt unwelcome or uncomfortable in a public place (gym locker room, store, restaurant, etc., due to their sexual identity?
0% ----- 100%

Coping Behaviors (Round 4)

When experiencing stress & stigma during the past month, what % of the time did the typical lesbian cope by drinking alcohol?
0% ----- 100%

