The ability to compete as a couple against other couples			
The ability to send other players a "wink" or "nod"			
The ability to message other players			

Did you find taking part in the competition to be beneficial to you at all?

No

Yes

[IF YES]

[figure not shown]

Great! Please use the text box below to briefly describe how the competition was beneficial for you

Do you any other ideas about how LezParlay might be improved?

What would you like to see be different in the next version?

Last thing, we promise! Now that the summer is ending,
please answer the 5 drinking questions a final time.

SINCE THE BEGINNING OF JULY, ON AVERAGE, HOW MANY DAYS PER WEEK
HAVE **YOU** DRANK?

SINCE THE BEGINNING OF JULY, ON AVERAGE, HOW MANY DRINKS HAVE **YOU** HAD EACH
DAY YOU DRANK?

SINCE THE BEGINNING OF JULY, ON THE DAY YOU DRANK THE MOST, HOW MANY DRINKS DID YOU HAVE?

0 1 2 3 4 5 6 7 8 9 10 11 12+

HAD A HANGOVER OR ILLNESS

GOT IN A PHYSICAL OR VERBAL FIGHT

HAD PROBLEMS WITH GF/PARTNER

MISSSED A SOCIAL ENGAGEMENT OR EVENT

HAD PROBLEMS WITH FRIENDS OR FAMILY

PERFORMED POORLY AT WORK/SCHOOL

HAD PROBLEMS WITH MONEY

HAD AN UNWANTED OR REGRETTABLE SEXUAL EXPERIENCE

SINCE THE BEGINNING OF JULY, HOW MANY OF THE 8 THINGS ABOVE HAVE YOU EXPERIENCED DUE TO DRINKING/PARTYING?

SINCE THE BEGINNING OF JULY, WHEN YOU'VE EXPERIENCED STIGMA OR NEGATIVE EMOTIONS WHAT % OF THE TIME DID YOU DRINK ALCOHOL IN AN EFFORT TO FEEL BETTER?

0 10 20 30 40 50 60 70 80 90 100

[End of Survey Debriefing Statement]

A FINAL THANKS & DISCLOSURE...

Thanks again for helping us evaluate LezParlay! Before you go we wanted to give you some more information about the detailed results you received in the LezParlay as an Official Tester. In addition to getting your feedback and ideas for the next version of the competition, another goal of this study was to evaluate whether delivering results for health-related topics in LezParlay had any benefits for players' health and well-being. To fully examine this, we had to make sure that balanced groups of Official Testers received more and less health-related feedback.

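### The problems item in Appendix C counts eight problems but prints answers 0 to 7 only, and its drinking/partying attribution is looser than the alcohol topic it belongs to

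*Protocol*

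**What the plan says.** Appendix C of the Protocol gives the questions for the intervention and replay rounds. Under "Alcohol Use Questions (Round 3 & Replay Bonus in Round 7" there are three consumption items (days per week, usual drinks, peak drinks) and then a problems item. The problems item shows a list that starts with "HAD A HANGOVER OR ILLNESS" and asks "how many of the 8 things above has the typical lesbian experienced due to drinking/partying". The answers printed beneath it run from 0 to 7, and the next line is the heading "Stigma Questions (Round 3 & Replay Bonus in Round 7".

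The printed question is the perceived-norm version. The own-report version is covered by a general note at the head of the appendix: "Parallel Questions will also ask participants to report their own corresponding behavior/attitude/experience". Its answer options are not printed.

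Section 3 makes Round 3 the trial baseline and says that the replay answers in Round 7 "will act as the 2 month post-intervention follow-up for the purpose of the evaluation study RCT". The post-competition survey in Appendix D asks each participant about herself: "HOW MANY OF THE 8 THINGS ABOVE HAVE YOU EXPERIENCED DUE TO DRINKING/PARTYING". No answer options are shown there for this item.

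On outcomes, Section 1 says: "Analysis of LezParlay efficacy will focus on longitudinal changes in alcohol use and coping behaviors". Alcohol problems are not named as a separate outcome.

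**The concern.** Two features of the item do not fit its purpose.

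First, the scale is one value short. A count of eight yes/no problems can take the values 0 to 8. The printed list is the one used for the days-per-week item, where 7 is the true maximum.

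Second, the item asks for problems due to drinking/partying, and partying is not defined. A participant could count a fight, a money problem or a missed event that followed drug use or a night out without alcohol. The topic and its feedback concern alcohol.

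The other three Alcohol Use Questions measure consumption, so this is the only item in the set that measures harm. It also supplies intervention content: Section 3 says that feedback is shown for each question of a delivered topic, so the norm displayed for alcohol problems inherits both features. An analysis plan cannot recover an answer that was never offered, or separate causes that were merged when the data were collected.

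**Working it through.** **Count of problems against answers.** The problems listed in Appendix C are: hangover or illness; friends or family; fight; work or school; girlfriend or partner; money; missed social event; regrettable sexual experience. That is 8, which matches the 8 stated in the question. The answers printed are 0, 1, 2, 3, 4, 5, 6, 7: eight values with a maximum of 7. Values needed: 8 + 1 = 9 (0 to 8). The only missing value is 8. The usual-drinks and peak-drinks items end in an open top category; this one has neither an 8 nor an open top.

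**Does this reach the trial measure?** Section 3 says that players report their own answers and guess how others answered the same questions, and that the feedback charts show guess, own answer and actual average side by side. A shared scale is therefore the natural reading, but it is an inference, because the own-report options are not printed. For Appendix D only the wording point can be shown.

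**How many participants would score 8?** The Protocol gives no problem rates, so the inputs below are assumptions, applied to the planned 500 evaluation participants.

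With independent problems of equal probability p, P(8) = p^8:

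| p | P(8) | Expected of 500 |
|---|---|---|
| 0.1 | 0.00000001 | 0.000005 |
| 0.2 | 0.0000026 | 0.001 |
| 0.3 | 0.000066 | 0.03 |
| 0.5 | 0.0039 | 2.0 |

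With clustered problems (beta-binomial, mean m, intraclass correlation r), set a = m(1/r − 1) and b = (1 − m)(1/r − 1). Then P(8) is the product over k = 0 to 7 of (a + k)/(a + b + k):

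| m | r | P(8) | Expected of 500 |
|---|---|---|---|
| 0.1 | 0.2 | 0.08% | 0.4 |
| 0.1 | 0.4 | 0.82% | 4.1 |
| 0.2 | 0.2 | 0.34% | 1.7 |
| 0.2 | 0.4 | 2.3% | 11.5 |
| 0.3 | 0.2 | 1.0% | 5.1 |
| 0.3 | 0.4 | 4.8% | 23.9 |

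If each of these participants answers 7, the mean falls by 1 × P(8), which is at most about 0.05 problems over this range.

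**Attribution.** No arithmetic applies; the texts can be set side by side. The heading in Appendix C says alcohol use. The item beneath it says drinking/partying. The coping items in the same appendix keep substances apart: one asks about coping by drinking, another about coping by taking a drug. Where the plan wanted alcohol alone, it said so. Against that, the Appendix D survey introduces its closing items, this one among them, as five drinking questions, which steers the reader towards alcohol.

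**The case against.** The strongest case on the other side has four parts.

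- **The short scale is printed only for the norm guess.** There, a missing 8 means only that nobody can guess that the typical woman had all eight problems. A reader might infer that participants with all eight problems are certainly miscoded or lost at baseline and follow-up. The documents do not show this, because the own-report options are not printed in either appendix. The inference is reasonable and no more.
- **It may be a drafting slip or a loss in reading the PDF.** Section 14 accepts draft questionnaires, and a dropped final 8 cannot be fully excluded. The neighbouring lists look complete, however, so nothing points to a loss. A slip is also worth correcting before the item is programmed.
- **Drinking/partying reads as a colloquial pair.** Under an alcohol heading, after three drinking items, and called a drinking question in the survey, most respondents may take it to mean alcohol. This narrows the ambiguity but does not remove it.
- **No dilution can be quantified.** A reader might infer that non-alcohol problems, being untouched by alcohol feedback, shrink the apparent effect. For example, a true 20% reduction would show as 20% × (1 − 0.10) = 18% or 20% × (1 − 0.20) = 16%. The documents give neither the share nor the effect. The assumption of no effect on non-alcohol problems is also unsafe, because the alcohol+coping arm receives feedback on a topic that includes coping by drug use. This objection stands.

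**Conclusion.** The point holds as a minor instrument defect. In the text as printed, the answers cannot record the maximum of the count the question asks for, and the attribution is broader than the alcohol topic. That the own-report measure at Round 3 and Round 7 shares the short scale is an inference from the parallel-question note.

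The consequences are probably small. Few participants would score 8: about 0 to 2 of 500 with independent problems, and up to about 24 only under strong assumed clustering. Those ranges rest on assumed problem rates. The share of reported problems that have nothing to do with alcohol is unknown, so the wording point has no size that can be derived from the documents. Nor would it be right to call this a failure of a named trial outcome: the efficacy focus in Section 1 is alcohol use and coping, and the problems count is one of four items in the alcohol set.

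**What to change.** Before Round 3 opens:

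1. Add the answer 8 to the norm and own-report versions of the item for Rounds 3 and 7.
2. Confirm that the post-competition survey in Appendix D offers 0 to 8.
3. Attribute the problems to drinking alcohol in every version. If the present wording has to stay, report the result as drinking/partying-related problems rather than alcohol problems.

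The cost is minor re-programming of one item. No change to design, sample size or schedule is needed. Timing matters, because a scale or wording changed between Round 3 and Round 7 would make the two answers less comparable.

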Appendix D

LezParlay Post-Competition Feedback Survey

What is your current age in years?

Which best describes your sexual identity?

lesbian

bisexual

queer

For how many years has this been your sexual identity?

Which best describes your relationship status?

Are you Hispanic or Latinx?

What category best describes your race?

What is the highest level of education you have completed?

How did you hear about LezParlay?

Great, thanks!

Next, let us know how much you **DISLIKED** or **LIKED** each aspect of LezParlay...

	Disliked very much	Disliked	Neutral	Liked	Liked very much
The "stereotype challenge" concept					
The topics & questions					
The detailed results you received					
The ability to browse player profiles					
The ability to submit & vote on questions					
The ability to bet on your guesses being correct in some rounds					
Text messages from LezParlay					
Emails from LezParlay					
The leaderboards showing the Top 100 Scorers each round					
The ability to win money & get gift cards					

Would the potential changes listed below make you LESS likely, EQUALY likely, or MORE likely to play LezParlay in the future?

	LESS likely to play	EQUALY likely to play	MORE likely to play
The ability to download and play in a native iphone/android app			
More frequent rounds with fewer questions in each (i.e., 1 round per week with 3 questions each round)			
Your scores & stats visible to you in the app at all times			
Your scores and stats visible to other players at all times			
The ability to challenge another player & earn bonus points if you beat them			
Playing against a featured queer influencer/celesbian type each round & earning bonus points if you score higher than them			
The ability to connect your profile to your significant other's profile			
The ability to compete as a couple against other couples			
The ability to send other players a "wink" or "nod"			
The ability to message other players			

Did you find taking part in the competition to be beneficial to you at all?

No

Yes

[IF YES]

[figure not shown]

Great! Please use the text box below to briefly describe how the competition was beneficial for you

Do you any other ideas about how LezParlay might be improved?

What would you like to see be different in the next version?

Last thing, we promise! Now that the summer is ending,
please answer the 5 drinking questions a final time.

SINCE THE BEGINNING OF JULY, ON AVERAGE, HOW MANY DAYS PER WEEK
HAVE **YOU** DRANK?

SINCE THE BEGINNING OF JULY, ON AVERAGE, HOW MANY DRINKS HAVE **YOU** HAD EACH
DAY YOU DRANK?

SINCE THE BEGINNING OF JULY, ON THE DAY YOU DRANK THE MOST, HOW MANY DRINKS DID YOU HAVE?

0 1 2 3 4 5 6 7 8 9 10 11 12+

HAD A HANGOVER OR ILLNESS

GOT IN A PHYSICAL OR VERBAL FIGHT

HAD PROBLEMS WITH GF/PARTNER

MISSSED A SOCIAL ENGAGEMENT OR EVENT

HAD PROBLEMS WITH FRIENDS OR FAMILY

PERFORMED POORLY AT WORK/SCHOOL

HAD PROBLEMS WITH MONEY

HAD AN UNWANTED OR REGRETTABLE SEXUAL EXPERIENCE

SINCE THE BEGINNING OF JULY, HOW MANY OF THE 8 THINGS ABOVE HAVE YOU EXPERIENCED DUE TO DRINKING/PARTYING?

SINCE THE BEGINNING OF JULY, WHEN YOU'VE EXPERIENCED STIGMA OR NEGATIVE EMOTIONS WHAT % OF THE TIME DID YOU DRINK ALCOHOL IN AN EFFORT TO FEEL BETTER?

0 10 20 30 40 50 60 70 80 90 100

[End of Survey Debriefing Statement]

A FINAL THANKS & DISCLOSURE...

Thanks again for helping us evaluate LezParlay! Before you go we wanted to give you some more information about the detailed results you received in the LezParlay as an Official Tester. In addition to getting your feedback and ideas for the next version of the competition, another goal of this study was to evaluate whether delivering results for health-related topics in LezParlay had any benefits for players' health and well-being. To fully examine this, we had to make sure that balanced groups of Official Testers received more and less health-related feedback.

So, full disclosure, the topics you received detailed results on in Rounds 3 and 4 of the game were not totally random in the same way they were in all of the other rounds (where they were determined by the doors you chose to open). Instead, as an Official Tester you were randomized to receive a specific sequence of feedback in Rounds 3 and 4 and the doors you selected were fixed to open to either health-related topics or topics unrelated to health. So, we're not sure if the health-related detailed results were beneficial yet, but analyzing the data from this study will allow us to find out! We also plan to examine whether you all reported different types of psychological benefits and/or differential levels liking for aspects of the competition based on the sequences of detailed results you received.

If you are interested in finding out what we learn here please let us know by sending an email to [contact] and we'll be sure to send you a summary of results when they are ready. Thanks again for your participation!
